# 7.3.2. Study Stopping Rules

The study will be stopped if two subjects experience any Grade 4 (i.e., life-threatening consequences; urgent intervention indicated) adverse event thought to be related to study drug. The medical monitor will review the cases with the PI prior to the decision to terminate the study is made.

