#### **Study Stopping Rules**

The study will be stopped if two subjects experience a Grade 4 adverse event thought to be related to study drug.

Number of Subjects (Planned): The number of subjects planned for enrollment is 40.

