#### 12.2.1. Severity Assessment

The severity of AEs will be determined as described in Table 5.

Table 5:Adverse Events Severity Definition

Mild Grade 1	Ordinarily transient symptoms that do not influence performance of subject's daily activities. Treatment is not ordinarily indicated.
Moderate Grade 2	Marked symptoms sufficient to make the subject uncomfortable. Moderate influence on performance of subject's daily activities. Treatment may be necessary.
Severe Grade 3	Symptoms cause considerable discomfort. Substantial influence on subject's daily activities. May be unable to continue in the study and treatment may be necessary.
Life- threatening Grade 4	Extreme limitation in activity, significant assistance required; significant medical/therapy intervention required hospitalization probable.
Death Grade 5	Death.

When changes in the intensity of an AE occur more frequently than once a day, the maximum intensity for the event should be noted for that day. Any change in severity of signs and symptoms over a number of days will be captured by recording a new AE, with the amended severity grade and the date (and time, if known) of the change.

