## 12.5. Serious Adverse Events (SAEs)

An AE is considered serious if it meets one or more of the following criteria:

- Results in death
- Is life-threatening (i.e., a subject is at immediate risk of death at the time of the event, not an event where occurrence in a more severe form might have caused death)
- Requires inpatient hospitalization or prolongation of existing hospitalization
- Results in persistent or significant disability/incapacity
- Results in a congenital anomaly/birth defect
- Is another important medical event (see below).

Important medical events that do not result in death, are not life-threatening, or do not require hospitalization may be considered SAEs when, based on appropriate medical judgment, they may jeopardize the subject and may require medical or surgical intervention to prevent one of the outcomes listed above. Examples of such medical events include allergic bronchospasm requiring intensive treatment in an emergency room or in a physician's office, blood dyscrasias or seizures that do not result in inpatient hospitalization, and the development of drug dependency or drug abuse. A distinction should be drawn between serious and severe AEs.

Severity is a measure of intensity whereas seriousness is defined by the criteria above. For example, a mild degree of gastrointestinal bleeding requiring an overnight hospitalization for monitoring purposes would be considered an SAE, but is not necessarily severe. Similarly, an AE that is severe in intensity is not necessarily an SAE. For example, alopecia may be assessed as severe in intensity, but would probably not be considered an SAE.

A blood sample for MN-001 concentration will be obtained when a subject experiences a SAE.

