## **12.5.1.** SAE Reporting Requirements

The PI or an authorized delegate is responsible for faxing the requested information to the Sponsor or designee within 24 hours or as soon as possible after learning of the event. Following the end of the subject's participation in the study, the PI or an authorized delegate should report SAEs "spontaneously" if considered at least possibly related to study medication.

Notification should be made by emailing a completed SAE Report Form to the Sponsor. Study sites in the US should email a completed SAE Report Form to:

[contact].As a minimum requirement, the initial notification should provide the following information:

- Study number
- Subject number
- Gender
- Date of birth
- PI's name and full study site address
- Details of SAE
- Criterion/criteria for classification as "serious"
- Study medication name, or code if blinded, and treatment start date
- Date of SAE onset
- Causality assessment (if sufficient information is available to make this classification).

Initial reports of SAEs must be followed later with detailed descriptions, including clear photocopies of other documents as necessary (e.g., hospital reports, consultant reports, autopsy reports, etc.), with the study subject's personal identifiers removed. All relevant information obtained by the PI or an authorized delegate through review of these documents will be recorded on the AE eCRF page and/or a new SAE Report Form and faxed to the Sponsor or designee within 24 hours of receipt of the information. If a new SAE Report Form is faxed, the PI must sign and date the form. The Sponsor may also request additional information on the SAE, which the PI or an authorized delegate must fax to the Sponsor or designee within 24 hours of the request using a new SAE Report Form, bearing the PI's signature and date.

Any AE fulfilling the criteria for expedited reporting will be reported by the Sponsor to regulatory authorities and Investigators and IEC(s) in accordance with the Sponsor's standard operating procedures (SOPs) and local regulatory requirements.

PIs should report all Investigational New Drug Application safety alerts received from the Sponsor to their local IRB/IECs.

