### DEFINITIONS

Adverse Event	An adverse event (AE) is any untoward medical occurrence in a subject administered a pharmaceutical product, regardless of causality assessment.		
Full Analysis Set Population	Group of randomized subjects who received at least 14 days of study drug and had at least one post-dose efficacy measurement.		
Safety Analysis Set Population	Group of subjects who received at least one dose of study drug and had at least one post-dose safety assessment.		
PK population	PK sample collection of the first 6 subjects enrolled in the study.		
Serious AE	An AE occurring at any dose that: results in death; is a life-threatening experience; requires inpatient hospitalization or prolongation of an existing hospitalization; results in a persistent or significant disability/incapacity; or is a congenital anomaly/birth defect in the offspring of a patient who received study drug.		
Treatment- emergent AE	AEs occurring from the time of first dose through 7 days after the last dose or that is already present prior to the first dose of study drug and becomes more severe post-dose		

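### The only numeric study-level stopping trigger names Grade 4 without 'or higher', so read literally a related death with no Grade 4 stage does not count

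*Combined protocol and SAP*

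**What the plan says.** The protocol states one numeric rule for stopping the whole study, in two places.

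- Synopsis, Study Stopping Rules: "The study will be stopped if two subjects experience a Grade 4 adverse event thought to be related to study drug".
- Section 7.3.2: "The study will be stopped if two subjects experience any Grade 4 (i.e., life-threatening consequences; urgent intervention indicated) adverse event", again limited to events judged related to the drug. It then adds a review step: "The medical monitor will review the cases with the PI prior to the decision to terminate the study is made".

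Table 5 in 12.2.1 has five severity grades. Grade 4 is labelled life-threatening and described by extreme limitation, significant intervention and probable hospitalization. Grade 5 is death, on its own row. The text below the table says: "Any change in severity of signs and symptoms over a number of days will be captured by recording a new AE". It also says that when intensity changes more than once in a day, the day's maximum is noted.

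The SAP sets no stopping threshold of its own.

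**The concern.** A stopping rule exists so that a count fixed in advance, rather than judgement under pressure, prompts the decision. Here the count is tied to one named grade, and the protocol's own severity table puts the worst outcome in a different grade. Someone applying the rule exactly as written would count two subjects who survived life-threatening related events. That person would not count two subjects who died abruptly from related events with no Grade 4 stage.

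At stake is whether the one numeric safety threshold covers related deaths in all cases, or whether some deaths depend wholly on discretionary routes.

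**Working it through.** The plan states no operating characteristic for the rule, so there is no figure to reproduce. The check is a reading of the text and a count.

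**Step 1: is there another numeric study-level trigger?**

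| Place | What it governs | Study-level event count? |
|---|---|---|
| Synopsis (Individual Stopping Criteria), 7.3.1, 8.6.3 | Single subjects | No |
| Synopsis (Treatment Phase), 6.1.2 | Review by an independent safety monitor | No |
| 6.1.2.1 | PK review before the dose increase | No |
| 7.3, 17.2 | Sponsor's right to stop | No |
| 12.5, 12.5.1 | SAE definition and reporting | No |
| SAP | Analysis only | No |

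The rule in the synopsis and 7.3.2 is the only one.

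**Step 2: which deaths fall outside the wording?**

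- Death after a Grade 4 stage on an earlier day: the change in severity is recorded as a new AE, so a Grade 4 event is on record and the subject counts.
- Grade 4 stage and death on the same day: only the day's maximum (Grade 5) may be recorded. The rule turns on what subjects experience, so the subject arguably counts, but someone tallying recorded grades could miss it.
- Death with no Grade 4 stage: Grade 5 only, so on a literal reading the subject does not count.

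**Step 3: the count.** Let G be the number of subjects with a related Grade 4 event, and D the number of other subjects with a related death and no Grade 4 stage. The threshold is 2.

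- Current wording, read literally: count = G.
- With 'Grade 4 or higher': count = G + D.

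| Case | Current wording | Grade 4 or higher |
|---|---|---|
| D = 2, G = 0 | 0, not met | 0 + 2 = 2, met |
| D = 1, G = 1 | 1, not met | 1 + 1 = 2, met |
| D = 1, G = 0 | 0, not met | 0 + 1 = 1, not met |
| D = 0, G = 2 | 2, met | 2 + 0 = 2, met |

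The first two cases change. A single abrupt related death stays a matter of discretion under either wording. The documents give no rate for related Grade 4 events or for such deaths, so no probability is attached.

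**The case against.** The strongest reply is that named grades in this protocol are floors. The individual stopping rules (synopsis and 7.3.1) also name bare grades: Grade 2 nausea or diarrhea beyond 3 consecutive days, and Grade 3 abdominal pain beyond 1 day. Read as ceilings, they would keep a subject with a week of Grade 3 diarrhea, or with Grade 4 abdominal pain, on treatment. Nobody would intend that, and by the same logic Grade 4 in 7.3.2 means Grade 4 or worse. SAP 13.1 points the same way: its severity categories end at life-threatening, so a fatal event would have to sit in that top category.

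Much of this stands, and Grade 4 or higher was probably meant. The SAP point is weaker, because the severity lists are loose at the upper end: protocol 13.1.4 stops at severe although Table 5 has five grades. Probable intent does not remove the ambiguity, since Table 5 separates the grades and the rule names only one.

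The practical reply also largely stands. SAEs are to be reported within 24 hours or as soon as the site can (12.5.1), an independent safety monitor reviews data regularly (6.1.2), and the sponsor may stop the study (7.3, 17.2). The trigger itself leads to a review, not an automatic halt. These routes make inaction after a related death unlikely, but none sets a count.

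A reader might go further and infer from the serious-event definitions that life-threatening cannot include death. Protocol 12.5 lists "Results in death" apart from "Is life-threatening (i.e., a subject is at immediate risk of death at the time of the event", and the SAP definition runs "An AE occurring at any dose that: results in death; is a life-threatening experience". The documents do not support that inference. Under 12.5 an event is serious if it meets any criterion and may meet several, so separate entries do not show that the categories exclude each other. Only Table 5 supports the literal reading.

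**Conclusion.** The point holds as a minor wording defect. Followed exactly as written, the only numeric study-level trigger gives 0 of 2 for two related deaths with no Grade 4 stage, and 1 of 2 for one such death plus one related Grade 4 subject. This rests on the absence of 'or higher' in both statements of the rule and on the separate Grade 5 in Table 5. It assumes that the events are in different subjects and are judged related.

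A reader might infer that the plan deliberately leaves deaths out, or that the study would carry on after related deaths. Neither follows. The likely intent covers death, most deaths preceded by a life-threatening stage already count, and the discretionary routes remain. What the plan lacks is a count that plainly includes every related death.

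**What to change.** In both the synopsis and 7.3.2, set the severity condition to 'Grade 4 or higher (including death, Grade 5)', leaving the number of subjects and the relatedness condition as they are. In 7.3.2, keep the bracketed gloss directly after 'Grade 4', and keep the medical monitor and PI review before any decision to terminate.

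The cost is an amendment approved by the sponsor and the IRB (17.1) and a slightly more sensitive trigger, which differs from the current wording only when a related death has occurred. Endpoints, visits, analyses and the meaning of Grade 4 do not change. A stricter rule that stops on any single related death is possible, but it is a separate choice and is not needed to close this gap.

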### 7.3.3. Follow-up Procedures Upon Discontinuation/Withdrawal

A termination CRF page should be completed for every subject who received study medication whether or not the subject completed the study. The reason for discontinuation should be indicated on the CRF. Any AEs that are present at the time of discontinuation/ withdrawal should be followed in accordance with the safety requirements outlined in Section 11.

# 8. TREATMENT OF SUBJECTS

# 8.1. Description of Study Drug

MN-001 will be provided in bottles and will be stored at room temperature.

# 8.2. Concomitant Medications

Concomitant medications required for the treatment of symptoms and signs of baseline disease (e.g., hypercholesterolemia, Type 2 diabetes) are permitted except as excluded below.

Concomitant medications for treatment of adverse events may be allowed. Subjects will be instructed to contact a member of the study staff prior to taking any medication.

Based on data *in vitro* CYP enzyme studies, MN-001 and MN-002 could potentially inhibit the metabolism of concomitantly administered drugs, particularly the concomitant drugs that are substrates of CYP2C8 and CYP2C9.

# 8.3. Prohibited Medications

The following medications are **prohibited** prior to and during study participation:

- CYP2C8 substrate with narrow therapeutic index (e.g., paclitaxel) within 15 days prior to study drug dosing and throughout the study
- CYP2C9 substrate with narrow therapeutic index (e.g., phenytoin, S-warfarin, tolbutamide) within 15 days prior to study drug dosing and throughout the study
- Macrolides and other antibiotics within 15 days prior to study drug dosing and throughout the study unless administered for a short-term treatment course during the study.
- Steroids within 30 days prior to study drug dosing and throughout the study unless administered for a short-term treatment course during the study

The medical monitor should be consulted prior to administration of a prohibited concomitant medication.

# 8.4. Treatment Compliance

Compliance will be monitored closely at each visit. Subjects will be instructed to bring all unused study medication with them to each visit. Compliance will be assessed by counting capsules and dividing the actual number of doses taken (per capsule count) by the number of doses the subject should have taken within a visit period and multiplying by 100. All subjects will be reminded of the importance of strict compliance with taking study medication for the effectiveness of treatment and for the successful outcome of the study. Subjects who miss more than 25% of scheduled doses or take more than 125% of the scheduled doses will be considered noncompliant and may be discontinued from the study per investigator's judgment.

# 8.5. Randomization and Blinding

This study is an open-label study; randomization and blinding are not applicable.

# 8.6. **Dosing Guidelines**

# 8.6.1. Treatment Phase

On Day 1, once baseline assessments are completed, subjects will be administered their first dose (one MN-001 250 mg tablet) of study drug in the clinic. Subjects will continue to take study drug once daily for 4 weeks and will increase the dose to 250 mg bid (500 mg/d) for 8 weeks.

# 8.6.2. Abnormal Laboratory Values

Laboratory tests should be repeated within 48 hours\* after any of the following laboratory values are met:

• Develop elevations of AST or ALT greater than 2 times baseline values (BLM) or total bilirubin (TBL) is greater than 1.5 X BLM

If there are persistent elevations in ALT or  $AST > 2 \times BLM$  or TBL >than 1.5  $\times BLM$ , then close observation by a hepatologist, repeat further laboratory tests, and physical examination 2-3 times per week should be initiated in order to identify the cause of liver function deterioration (i.e. potential of drug-induced liver injury (DILI).

(\*If a patient resides in a remote area, they can be tested locally and the results be communicated to the investigator site promptly)

# 8.6.3. Dosing Interruption for Abnormal Laboratory Values

If the laboratory values are any of the following, then the **subjects should stop study medication**. When baseline values were:

- < 2X ULN, discontinue if ALT or AST increases to >5X BLM.
- $\geq$  2X ULN but <5X ULN, discontinue if ALT or AST increases to >3X BLM
- $\geq$  5X ULN, discontinue if ALT or AST increases to >2X BLM
- Discontinue if ALT or AST increase >2X BLM AND the increase is accompanied by a concomitant TBL increase to >2X BLM OR the INR concomitantly increases by >0.2.

While dosing is withheld, subjects will continue tests and assessments according to the schedule defined in the protocol (and may also undergo additional assessments to evaluate the laboratory abnormality as per the Investigator's standard practice). In addition, subjects must have the abnormal laboratory result rechecked at least every 2 weeks (rechecks will be run at the local laboratory if a patient lives remote area) until resolution or stabilization of the laboratory value.

After laboratory values return within normal limits, resumption of blinded study treatment is to be considered on a case by case basis and must be discussed with the Independent Medical Monitor.

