# Individual Stopping Criteria

Subjects who experience an adverse event of Grade 2 nausea and/or diarrhea for greater than 3 consecutive days or Grade 3 nausea and/or vomiting for greater than 1 day thought to be related to study drug will be discontinued from the study. Additionally, subjects who experience an adverse event of Grade 3 abdominal pain lasting for greater than 1 day thought to be related to study drug will be discontinued from the study.

Additionally, study drug will be discontinued or temporarily interrupted under the following

conditions:

- When the baseline values were <2X ULN, discontinue if ALT or AST increases to >5X baseline value (BLM).
- When the baseline values were  $\geq$ 2X ULN but <5X ULN, discontinue if ALT or AST

increases to >3X BLM

- When the baseline values were  $\geq$ 5X ULN, discontinue if ALT or AST increases to >2X BLM
- Discontinue if ALT or AST increase >2X BLM AND the increase is accompanied by a concomitant total bilirubin (TBL) increase to >2X BLM OR the INR concomitantly increases by >0.2

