# 7.3. Subject Withdrawal/Discontinuation Criteria

Subjects may request to be withdrawn from the study at any time for any reason.

The Investigator may interrupt the treatment of any subject whose health or well-being may be compromised by continuation in the study. The following instances require subjects to be withdrawn from the study:

- Subject fails to adequately comply with the dosing, evaluations, or other requirements of the study at the discretion of Investigator.
- Subjects who have adverse events or abnormal laboratory tests that require discontinuation of study medication;
- Subjects who, in the opinion of the Investigator, should be discontinued for their wellbeing;
- Subjects who are no longer able to understand task instructions or to perform tests adequately.
- Subject becomes pregnant during the study. See section 12.7 for reporting requirements and follow-up of the pregnancy.

If a subject withdraws or is removed from the study for any reason, the reason and date of discontinuation of study medication should be recorded in the appropriate section of the Case Report Form (CRF). At the time of study discontinuation, every effort should be made to ensure all Early Termination (ET) procedures and evaluations are performed.

The study sponsors reserve the right to discontinue the study at any time for medical or administrative reasons.

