# 7.3.1. Individual Stopping Criteria

Subjects who experience an adverse event of Grade 2 nausea and/or diarrhea for greater than 3 consecutive days, or Grade 3 nausea and/or vomiting for greater than 1 day thought to be related to study drug will be discontinued from the study. Additionally, subjects who experience an adverse event of Grade 3 abdominal pain lasting for greater than 1 day thought to be related to study drug will be discontinued from the study.

Subjects with abnormal laboratory tests should be discontinued or study drug temporarily interrupted. Please see section 8.6.2 and 8.6.3 for details.

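### The same liver-test trigger leads to discontinuation, interruption or study withdrawal depending on the section read, and the restart sentence does not fit the baseline bands beside it

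*Combined protocol and SAP*

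**What the plan says.** Four places in the protocol govern what follows a liver-test signal.

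- **Section 8.6.3**, whose heading speaks of dosing interruption, opens with "If the laboratory values are any of the following, then the subjects should stop study medication". Each threshold is then worded as discontinuation, for example "discontinue if ALT or AST increases to >3X BLM" for a baseline of 2 to below 5 times ULN. The text goes on: "While dosing is withheld, subjects will continue tests and assessments according to the schedule defined in the protocol". Rechecks run at least every two weeks until the value resolves or stabilizes. The restart sentence is "After laboratory values return within normal limits, resumption of blinded study treatment is to be considered on a case by case basis", with discussion with the Independent Medical Monitor required.
- **Synopsis, Individual Stopping Criteria**, lists the same thresholds under the words "study drug will be discontinued or temporarily interrupted under the following".
- **Section 7.3.1** says "Subjects with abnormal laboratory tests should be discontinued or study drug temporarily interrupted" and refers to 8.6.2 and 8.6.3 for detail.
- **Section 7.3** says "The following instances require subjects to be withdrawn from the study" and includes in its list "Subjects who have adverse events or abnormal laboratory tests that require discontinuation of study medication". It asks for every effort to complete the ET procedures.

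The Early Termination visit in 8.8.1 applies to subjects who have discontinued study medication. It includes the lipid panel, efflux sample and liver MRI. Both schedule tables merge it with the Week 12 column.

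SAP 6.2 makes triglycerides at Week 8 and efflux at Week 12 co-primary; protocol 10.1 places triglycerides at 12 weeks. SAP 6.2 also lists as secondary outcomes treatment discontinuation for any reason, due to treatment-emergent events, and due to treatment-related events.

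**The concern.** The same laboratory result carries different instructions in different sections. This affects three things.

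1. **A safety action.** Two sites with identical results could act differently, and each could cite the protocol.
2. **The safety counts.** The SAP counts treatment discontinuations as outcomes, and listing 16.2.7.3 names study discontinuation and drug interruption as separate categories. The status a site assigns decides where the subject appears.
3. **The efficacy data.** A subject kept on schedule supplies Week 8 and Week 12 values, some of them off drug. A withdrawn subject supplies one ET value at the time of stopping. These are different measurements, and they come from the subjects who matter most for the liver-safety question.

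The restart sentence adds a second mismatch. Stopping is judged against the subject's own baseline, while restarting is judged against the normal range. The sentence also mentions blinded treatment, although 8.5 says blinding does not apply, so its wording does not fit this trial.

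**Working it through.** The documents give no figure to reproduce on this point. The check sets the texts side by side and then applies arithmetic to the bands in 8.6.3.

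**Step 1: consequences stated for the same trigger.**

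| Place | Drug | Participation and visits |
|---|---|---|
| 8.6.3, threshold bullets | Stop, discontinue | Not stated |
| 8.6.3, text after the bullets | Withheld, may resume | Scheduled assessments continue |
| Synopsis and 7.3.1 | Discontinue or interrupt, no criterion | Not stated |
| 7.3 with the ET section | Discontinued | Withdrawn from study, ET visit |

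Section 7.3.1 sends the reader to 8.6.2 and 8.6.3 for detail. Section 8.6.2 covers retesting and observation only. Section 8.6.3 does not say which triggers are permanent. If discontinue means the same thing in 8.6.3 and 7.3, every threshold in 8.6.3 requires withdrawal, and the withheld-dosing text never applies.

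**Step 2: restart condition against the bands.** Inputs: the stopping multiplier is 5 for a baseline below 2 times ULN, 3 for 2 to below 5, and 2 for 5 or above (8.6.3). Entry excludes ALT or AST above 10 times ULN and total bilirubin above 1.5 times ULN (7.2.2). For baseline *b* in multiples of ULN:

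- stopping level = multiplier × *b*
- fall below own baseline needed to reach 1 × ULN = 1 − 1/*b*, or zero if *b* ≤ 1

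| Baseline ALT/AST (× ULN) | Stops above (× ULN) | Fall below baseline needed |
|---|---|---|
| 1 | 5 × 1 = 5 | 0% |
| 1.5 | 5 × 1.5 = 7.5 | 1 − 1/1.5 = 33% |
| 2 | 3 × 2 = 6 | 1 − 1/2 = 50% |
| 3 | 3 × 3 = 9 | 1 − 1/3 = 67% |
| 5 | 2 × 5 = 10 | 1 − 1/5 = 80% |
| 10 (entry ceiling) | 2 × 10 = 20 | 1 − 1/10 = 90% |

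The same formula for total bilirubin at its entry ceiling gives 1 − 1/1.5 = 33%. A subject with a raised baseline who recovers fully to that baseline does not meet the restart condition. Rechecking may end when the value stabilizes, so such a subject can leave rechecking without having met it.

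**Step 3: effect on the data.** Take a subject who crosses a threshold at Week 4. On the withheld-dosing route, the Week 8 triglyceride and the Week 12 efflux and MRI are collected on schedule. On the withdrawal route, lipids, efflux and MRI are taken once, near Week 4, and there is no Week 8 visit. The SAP does not say whether an ET value stands in for Week 8 or Week 12, or whether an off-drug value enters the mean change. Protocol section 13 says the SAP will contain sensitivity analyses for dropouts; the SAP has none.

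**Step 4: scale.** One subject is 1/40 = 2.5% of the protocol's sample size, or 1/20 = 5% of the lower end of the SAP's anticipated enrollment. The documents give no trigger rate. If it is assumed, for illustration only, to lie between 1% and 10% per subject, the chance of at least one trigger is 1 − (1 − *p*)^*n*:

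- *n* = 40: 33.1% to 98.5%
- *n* = 20: 18.2% to 87.8%

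**The case against.** The strongest reply is that a coherent reading exists. Section 8.6.3 is about interruption and describes a sequence of stop, recheck and possible restart. Section 7.3 separately lets the investigator interrupt treatment, so its withdrawal clause could be confined to permanent cessation. This reading works only if discontinue means a pause in 8.6.3 and a permanent stop in 7.3. Nothing in the protocol says so, and the synopsis and 7.3.1 present the two actions as alternatives. The objection shows what the sponsor may have meant, but it does not remove the conflict.

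Three further objections stand, because they limit stronger readings that a reader might infer.

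- **That restart is impossible for subjects with raised baselines.** It is not. Enzymes can fall below baseline, and liver enzymes are a secondary efficacy measure on which improvement would be of interest. With a normal baseline the condition asks only for recovery. It may also be deliberately strict; the documents do not show that it is a mistake.
- **That dosing and Week 12 data collection are undefined.** They are not. Restart is case by case with the Independent Medical Monitor. Both visit routes plan lipids, efflux and MRI. The routes conflict mainly in timing and in whether a separate Week 8 visit takes place. The SAP also words the MRI change and the efflux listing as post-treatment, which might admit an ET value; but SAP 6.2 names Week 12 for efflux, and triglycerides are tied to Week 8.
- **That the restart rule fails for much of the trial population.** There is no support for this. No baseline distribution is given, entry sets no minimum ALT or AST, and the rule matters only after a threshold has been crossed.

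**Conclusion.** The point holds as a contradiction in the text. One trigger carries different consequences in 8.6.3, the synopsis with 7.3.1, and 7.3 with the ET section, and a site cannot comply with all of them. The restart sentence is out of line with the baseline-indexed bands in its own section and with the open-label design. The result is inconsistent classification in the discontinuation outcomes and two possible sets of efficacy values with no SAP rule for using them.

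The size is bounded rather than estimated: 2.5% to 5% of the data set per affected subject, with the number affected unknown. The required falls of 50% at 2 times ULN and 80% at 5 times ULN take the restart sentence literally, with normal limits meaning at or below 1 × ULN. The illustrative probabilities rest on an assumed trigger rate. No bias in the primary results is shown. The case for acting is that the rules conflict on a safety action and that reconciling them is cheap.

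**What to change.** 1. Reconcile the synopsis, 7.3, 7.3.1, 8.6.3 and the Early Termination section so that each laboratory trigger has one stated status: interruption, permanent discontinuation of drug, or withdrawal from the study. Use each term in one sense throughout.
2. Reconcile the restart sentence with the baseline bands and remove the reference to blinding. The thresholds and the restart rule are clinical matters for the sponsor; none is proposed here.
3. State one visit pathway for subjects who are off drug. For the analysis, the continued schedule that 8.6.3 already describes is preferable, because it keeps the Week 8 and Week 12 time points.
4. In the SAP, state how ET and off-drug values enter the Week 8 triglyceride and Week 12 efflux summaries, define interruption and discontinuation to match the protocol, and add the dropout sensitivity analyses that protocol section 13 promises.

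The cost is a wording amendment to the protocol and a short addition to the SAP. No new procedures are needed, since the visits and assessments are already scheduled.
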